Understanding that environmental factors can potently and sometimes rapidly, favorably or negatively influence epigenetic expression, a short-term diet and lifestyle intervention may significantly augment DNA methylation expression.

The purpose of this study is to evaluate a 9-week diet and lifestyle intervention on patient-reported quality of life, symptoms, and DNA and biochemical methylation-related biomarkers in healthy males ages 50-72.

B. SPECIFIC AIMS

B.1 Primary Aim:

To evaluate a 9-week diet and lifestyle intervention on patient-reported quality of life.

Hypothesis: Quality of life will improve as a result a 9-week diet and lifestyle intervention, relative to a wait-list control condition.

Outcome measure: Changes in patient-reported quality of life, measured by the PROMIS-29 (Patient-Reported Outcomes Measurement Information System-29) questionnaire.

B.2 Secondary Aim:

To evaluate changes in patient-reported symptoms after a 9-week diet and lifestyle intervention.

Hypothesis: Severity of patient-reported symptoms will decrease following a 9-week diet and lifestyle intervention.

Outcome measures: Changes in patient-reported symptoms, measured by the MYMOP (Measure Yourself Medical Outcome Profile) questionnaire, NUNM Multi-system side effects/symptoms questionnaire, and the Medical Symptom Questionnaire (MSQ).

Protocol

Study Title: Methylation Diet and Lifestyle (MDL) Study

PI: [name], ND, MPH and [name], ND

IRB #: RB100217

Approval Date: 2.9.18

Ver. 1.1

B.3 Tertiary Aim:

To assess changes in methylation at CpG sites of DNA after a 9-week diet and lifestyle intervention.

Hypothesis: Methylation at CpG sites associated with chronic inflammation will change after the 9-week diet and lifestyle intervention.

Outcome measure: Number of CpG methylation sites, measured by the Infinium MethylationEPIC Kit (Illumina, Inc.)

B.4 Exploratory Aims:

To evaluate changes in biomarkers associated with methylation.

Outcome measures: Changes in the methylation related biomarkers as measured by Doctor's Data Methylation Index Panel, Methylation Profile, and Folate Vitamer Panel.

C. BACKGROUND AND SIGNIFICANCE

C.1. Methylation background and significance

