This study is a preliminary randomized control trial evaluating a 9-week diet and lifestyle intervention on quality of life, patient-reported symptoms, and biomarkers associated with methylation. We will recruit forty-eight participants with 24 randomized to each study group. Refer to Figure 1 for an overview of the study flow.

Figure 1. Study Flow Overview

D.2 Study Intervention

Study participants will be randomized into an intervention or control group. The intervention group will undergo a 3-week washout period following the discontinuation of any non-medically required nutrition or herbal supplements. The intervention group will follow detailed diet and lifestyle recommendations over a 9-week period. Two webinars at the start of the

Protocol

Study Title: Methylation Diet and Lifestyle (MDL) Study

PI: [name], ND, MPH and [name], ND

IRB #: RB100217

Approval Date: 2.9.18

Ver. 1.1

intervention phase will provide information to participants on proper food and exercise choices, as well as how to access and use the required electronic resources (apps).

The control group will undergo the same testing measures as the intervention group, but will not have access to the education information or be instructed to change diet or lifestyle factors. They will have access to the information after the study is complete.

D.2.1 Diet Recommendations

Specific dietary guidelines will be outlined for participants and should include the following:

Per week	Per day

3 servings of liver
 
 • (1 serving = 3 oz) • Choose preferably organic liver 
5-10 eggs
 
 • Ideally free-range, organic, omega-3 enriched 	
2 cups of dark leafy greens
 
 • Measured raw, chopped, and packed • Including kale, Swiss chard, collards, spinach, dandelion, mustard greens • Does not include salad greens such as romaine, iceberg, Spring mix 
2 cups cruciferous vegetables
 
 • Measured raw, chopped, and packed • Including broccoli, cabbage, cauliflower, Brussels sprouts, bok choy, arugula, kale, watercress, rutabaga, kohlrabi, radish, turnip
General	

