Not all foods recommended and consumed during the study intervention may be captured by VioScreen. An additional food frequency questionnaire (FFQ), with approximately 250 foods and beverages, was created to assess consumption. It has been designed to be consistent with the validated block Brief FFQ by NutritionQuest. This will be administered electronically via RedCap online database to all study participants at Visits 1, 2, and 3.

D.2.7.5. Adherence phone calls

Participants will be contacted via phone once per week during the first 4 weeks of the study and every other week for the remainder of the study. Designated health coaches will assess for adherence to the study intervention including dietary, stress management, and exercise recommendations. Participants will be able to ask questions pertaining to the study intervention.

Refer to Appendix B for detailed script of these phone calls.

Protocol

Study Title: Methylation Diet and Lifestyle (MDL) Study

PI: [name], ND, MPH and [name], ND

IRB #: RB100217

Approval Date: 2.9.18

Ver. 1.1

D.3 Description of Participant Population

D.3.1. Participant Characteristics

Sample size: n=48

We will enroll and randomize up to 48 people which will allow for 20% attrition such that we have an evaluated sample size of 40 to allow for withdraws or dropouts.

Age: 50-72

Gender: Males only

Minorities: all racial and ethnic backgrounds will be recruited from the general population without preference or discrimination.

Vulnerable Populations (e.g. children, pregnant women, cognitively impaired): No vulnerable populations will be enrolled.

D.3.2. Inclusion and Exclusion Criteria

Individuals must meet the following participation criteria:

Inclusion criteria:

- Males, ages 50-72
- Willing to adhere to 9 weeks of a dietary and lifestyle program including specific nutrition and exercise guidelines
- Willing to avoid any over-the-counter medications, supplements or herbal products for the length of the study, except short-term use (<1 week) use at least 1 week before scheduled study visits
- Willing to have blood drawn three times and abstain from food or beverage intake for 10-12 hours before blood draws
- Willing to provide saliva samples
- Willing to track food intake, sleep, stress management techniques, and exercise daily
- Willing to drink a nutrient-enriched beverage and take a encapsulated probiotic daily
- Willing and able to use electronic devices and connect to the internet

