Measure Yourself Medical Outcome Profile (MYMOP) is a patient centered outcome measure that allows for the participant to self-select their top health concern(s) or symptom(s) they are dealing with in their own words. The participant can also choose an activity that is limited by that health concern. The participant is then asked about their own general wellbeing. Each of these questions is scored on a 0-6 scale. The medications that the participant is taking related to the specific symptoms and their desire to cut down the medication is also recorded.

Scoring of the MYMOP is an average of all of the profile questions answered. Participants only have to choose one symptom and answer the well-being profile question. If a second related symptom and activity level are identified all of the scores are included in the average final score.

MYMOP has been shown to be an effective outcome measurement for health concerns, especially in a diverse population and has more sensitivity to change compared to the SF-36.^{29,30}

D.4.2.2. Secondary Measure: NUNM Multi-system Symptom/Adverse Events Questionnaire

The NUNM Multi-system Symptom/Adverse Event Questionnaire is a standardized ninety-one point monitoring form that requires asking questions pertaining to the following organ systems: eyes/ears/nose/throat, gastrointestinal, neurological/ musculoskeletal, psychological/general, cardiopulmonary, skin, genitourinary and whole body systems.

Table 3. Grading of Items on the NUNM Adverse Event Monitoring Form	
Grade	Definition
0=Not Present	No AE, Function within normal limits
1=Mild; asymptomatic or mild symptoms; clinical or diagnostic observations only; no intervention	No intervention; asymptomatic lab or radiographic findings; marginal clinical significance
2=Moderate; minimal, local or noninvasive intervention indicated	AE limited activities of daily living (ADLS)
3=Severe or medically significant but not immediately life-threatening	AE significantly limited basic self-care, AE required initial hospitalization or prolongation of hospitalization
4=Life-threatening	Life-threatening consequences AE
5=Fatal	Fatal AE

Changes in a current symptom(s) by a grade of 2 or higher, or a new symptom(s) graded 2 or higher will be included in analysis to compare symptom changes between groups.

Protocol

Study Title: Methylation Diet and Lifestyle (MDL) Study

PI: [name], ND, MPH and [name], ND

IRB #: RB100217

[figure not shown]
Approval Date: 2.9.18

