Ver. 1.1

D.4.3. Tertiary Outcome: Changes in methylation at CpG sites of DNA

The tertiary outcome will be the assessment of methylation changes at “CpG” sites on DNA using a commercial available assay kit. CpG sites are sites on DNA in which a cytosine base is separated from a guanine base by only one phosphate; CpG sites are known sites for regulation by methylation. The Infinium MethylationEPIC Kit by Illumina uses the latest technology to assess methylation status of over 850,000 DNA sites across the genome. Using DNA provided from a saliva sample, this assay measured changes in methylation at “CpG” sites of DNA, i.e., whether or not sites for methylation are, or are not, methylated. For a given time point, the degree of methylation at each site (i.e., β) is presented as a color ranging from “green” (i.e., $\beta = 0$, low methylation) to “red” (i.e., $\beta = 1$, high methylation). We will compare the methylation state of participants at baseline to their status at the end of the study. “Differential” methylation is considered a change in CpG site methylation of $\Delta\beta \geq 0.66$. See Figure 2 below for a typical representation of the results of the assay.²⁸

Figure 2: Typical Demonstration of Results Applying the Infinium MethylationEPIC Kit

A saliva sample will collect approximately 2 mL (~1 teaspoon) into a cryovial. Saliva samples will be labeled only with a study ID, date of collection, and visit number and frozen to -70 °C.

At the conclusion of the study, all samples will be batched shipped to: Yale University Center for Genome Analysis Attn: [name], Associate Director of Microarray; [name].

D.4.4. Exploratory Outcomes: Changes in biomarkers associated with methylation

D.4.4.1. Methylation Profile – Doctor’s Data

Protocol

Study Title: Methylation Diet and Lifestyle (MDL) Study

PI: [name], ND, MPH and [name], ND

IRB #: RB100217

Approval Date: 2.9.18

Ver. 1.1

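### The only CpG comparison worded in D.4.3 is baseline to end of study with no arm contrast named, and the unexplained 0.66 cut-off for differential methylation excludes decreases as written and mid-range sites in any case

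*Protocol*

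**What the plan says.** The tertiary outcome is described in Protocol D.4.3. Its one statement of a comparison is: "We will compare the methylation state of participants at baseline to their status at the end of the study". The same section gives beta a range from 0 (low methylation) to 1 (high methylation) and then sets a rule: differential "methylation is considered a change in CpG site methylation of" delta-beta at least 0.66, with no absolute-value sign.

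B.3 gives the outcome measure as "Number of CpG methylation sites, measured by the Infinium MethylationEPIC Kit". Its hypothesis is that methylation at inflammation-related sites will change after the intervention. It names neither a direction nor the control group. G.4 contains no CpG analysis.

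Elsewhere the protocol describes a two-arm randomised design:

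- B.1 states the primary hypothesis "relative to a wait-list control condition".
- D.1 describes a randomised trial "evaluating a 9-week diet and lifestyle intervention on quality of life, patient-reported symptoms, and biomarkers associated with methylation".
- D.2 says "The control group will undergo the same testing measures as the intervention group".
- Table 4 schedules the EPIC array at Visits 1 and 3, without distinguishing the arms.
- G.4 compares PROMIS-29 and MYMOP changes between groups and treats the MSQ like PROMIS-29. D.4.2.2 says that NUNM symptom changes "will be included in analysis to compare symptom changes between groups".

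**The concern.** Two things in D.4.3 sit badly with the rest of the protocol.

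The first is the comparison. Section F presents the expected gain as proof-of-concept data that diet and lifestyle are efficacious in altering epigenetic signalling. A change from baseline to Week 9 does not show that by itself. Assay variation, season, repeated testing or simply time could produce it. The randomised control arm exists to remove these explanations, and its samples are already in the schedule, but the only worded CpG comparison does not call on them.

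The second is the cut-off. A change of 0.66 is two thirds of the whole scale. If it decides which sites enter the B.3 count, the trial could report no differential methylation when real changes of moderate size had occurred.

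**Working it through.** **Comparison: the text side by side**

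| Outcome | Aim names the control? | Between-group comparison stated? |
|---|---|---|
| PROMIS-29 | Yes (B.1) | Yes (G.4) |
| MYMOP | No (B.2) | Yes (G.4) |
| MSQ | No (B.2) | Analysed similarly to PROMIS-29 (G.4) |
| NUNM questionnaire | No (B.2) | Yes (D.4.2.2) |
| CpG methylation | No (B.3) | No; baseline against end of study (D.4.3) |

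B.2 shows that an aim silent on the control can still be analysed between arms. CpG methylation differs from the four questionnaires because no other section supplies the contrast.

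**Cut-off: exact bounds, no assumptions beyond the 0 to 1 scale**

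The 0.66 cannot be reproduced, because the protocol gives no standard deviation (SD), assay error, expected effect or derivation for it. Its consequences can be worked out.

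- A rise of at least 0.66 needs baseline + 0.66 ≤ 1, so baseline ≤ 1 − 0.66 = 0.34.
- A fall of at least 0.66 needs baseline − 0.66 ≥ 0, so baseline ≥ 0.66.
- A site with baseline strictly between 0.34 and 0.66 can do neither. The excluded band is 0.66 − 0.34 = 0.32 wide.
- Taken literally, delta-beta ≥ 0.66 is met only by increases, so only sites starting at or below 0.34 could ever qualify.

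**Illustration: assumed SDs, not from the protocol**

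D.3.1 plans that "we have an evaluated sample size of 40", taken here as 20 per arm. The SD of change in beta is assumed to be 0.05, 0.10, 0.15 or 0.20. For one site, with a two-sided two-sample t test, 80% power and noncentral t, the detectable difference in mean change is 0.909 × SD at alpha 0.05. It is 2.447 × SD at alpha 0.05/850,000 = 5.9 × 10⁻⁸ (Bonferroni).

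| Assumed SD | Detectable, alpha 0.05 | Detectable, Bonferroni | Power for a true shift of 0.30, Bonferroni | Chance one man's change reaches 0.66, true shift 0.30, normal model |
|---|---|---|---|---|
| 0.05 | 0.05 | 0.12 | above 99.9% | below 0.001% |
| 0.10 | 0.09 | 0.24 | 98.6% | 0.02% |
| 0.15 | 0.14 | 0.37 | 39% | 0.8% |
| 0.20 | 0.18 | 0.49 | 6% | 3.6% |

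The last column is P(Z ≥ (0.66 − 0.30)/SD). If the rule applied to the mean of 20 men, the chance would be at most 4.1 × 10⁻¹⁶. The detectable difference reaches 0.66 only at an SD of 0.66/2.447 = 0.27 (Bonferroni) or 0.66/0.909 = 0.73 (alpha 0.05). These figures show scale only. The SDs and the 0.30 shift are assumed, and a significance test is being set beside a magnitude label.

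**The case against.** **On the comparison.** The sentence stands under Outcome Measures, not Statistical Analysis, and may only identify the two time points that form the change. The participants it mentions can be those of both arms. B.2 is as silent on the control as B.3, yet its measures are compared between groups. A tertiary array model is commonly left to the SAP, which is not shown. All of this stands. A reader might infer that the protocol commits itself to a within-group analysis or discards the control data. The text does not support that, and the missing model and multiplicity rule are not faults here. What remains is that the one comparison the protocol does word names no arm contrast.

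**On the cut-off.** D.4.3 speaks of sites being or not being methylated. If a change of state is meant, moving from 0.34 or below to 0.66 or above would be a natural definition, and leaving out mid-range sites would follow from it. The next sentence points to Figure 2 and a cited validation of the array; neither can be checked here, and the citation is attached to the figure rather than to the 0.66. The word change may have been meant to cover both directions. So a reader might infer that 0.66 is wrong, but the documents do not show that. A reader might also infer that the B.3 count uses 0.66. B.3 does not say so, although no other criterion for differential methylation is stated. Nothing says that smaller changes will go unreported, and beta values can be reanalysed at any threshold.

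**On the size.** The power and probability figures rest on assumed inputs and cannot prove the label wrong. That also stands.

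**Conclusion.** The point holds in a limited form. The text itself shows three things: the only worded CpG comparison names no arm contrast; the 0.66 rule as written counts no decreases, against a hypothesis without direction; and even as an absolute change it can never be met by a site with baseline beta strictly between 0.34 and 0.66. That moderate real changes would be missed is conditional on the B.3 count using 0.66. The detectable differences and probabilities are illustrations under assumed SDs and an assumed shift, not evidence from the protocol.

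The outcome is tertiary in a trial described as preliminary, and the PROMIS-29 conclusion is unaffected. The change is still worth making, because section F states the expected gain in terms of efficacy on epigenetic signalling and the control data that would support it are already planned.

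**What to change.** - In B.3 and D.4.3, state the tertiary contrast as the change in CpG methylation from Visit 1 to Visit 3 in the intervention arm relative to the wait-list control, for example Visit 3 beta adjusted for Visit 1 beta. The exact model and the multiplicity rule may go in the SAP.
- Do not let 0.66 decide which sites count as changed, and say in B.3 how the sites are counted.
- If 0.66 is kept, write it as |delta-beta| ≥ 0.66, give the reason for it, and use it only as a descriptive label.

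The cost is wording in two sections and a little more analysis. No new samples, visits or assays are needed, since the array is already scheduled at Visits 1 and 3 and the control group has the same tests.

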- Able to speak, read and understand English

Exclusion criteria:

- Currently taking any of the following prescription medications
 - Proton pump inhibitors: omeprazole (Prilosec, Prilosec OTC); aspirin and omeprazole (Yosprala); lansoprazole (Prevacid, Prevacid IV, Prevacid 24-Hour); dexlansoprazole (Dexilent, Dexilent Solutab); rabeprazole (Aciphex, Aciphex Sprinkle); pantoprazole (Protonix)

Protocol

Study Title: Methylation Diet and Lifestyle (MDL) Study

PI: [name], ND, MPH and [name], ND

IRB #: RB100217

Approval Date: 2.9.18

Ver. 1.1

- H2-blockers: nizatidine (Axid, Axid AR, Axid Pulvules); famotidine (Pepcid, Pepcid AC); cimetidine (Tagamet, Tagamet HB); ranitidine (Zantac)
- These classes of medications are excluded due to direct (due to nutrient requirements for metabolism) and indirect (through impaired digestion and assimilation of nutrients).
- Use of nutrition supplements or herbal products not prescribed by a licensed healthcare provider for a medical condition
- Currently following a prescribed dietary/lifestyle program or initiate within the 30 days prior to baseline
- Initiation of or changes to an exercise regimen within 30 days prior to baseline
- Use of nicotine, marijuana or cannabinoids (including CBD products) or recreational drugs/substances (such as but not limited to cocaine, phencyclidine [PCP], and methamphetamine) current/within the last 30 days or use during the study
- Have a diagnosis of cardiovascular disease, kidney disease, liver disease, diabetes, autoimmune disease, high blood pressure, or cancer (does not include *basal cell carcinoma, squamous cell carcinoma, and/or carcinoma in situ of the cervix*).
- Have a diagnosis of an immunodeficiency condition, such as Human Immunodeficiency Virus (HIV) infection or Acquired Immune Deficiency Syndrome (AIDS)
- Have a diagnosis of neurodegenerative conditions such as, amyotrophic lateral sclerosis (ALS), Parkinson’s disease, Multiple Sclerosis, or Alzheimer’s disease.
- Excessive alcohol consumption (more than 4 drinks per day or 14 per week on average)
- Known sensitivity, intolerance or allergy to ingredients in the study supplements or in the recommended dietary therapy
- Currently receiving intravenous nutrient therapy
- Currently participating in another interventional research study or participated in another interventional study within the last 3 weeks prior to baseline

D.4 Outcome Measures

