Study Title: Methylation Diet and Lifestyle (MDL) Study

PI: [name], ND, MPH and [name], ND

IRB #: RB100217

Approval Date: 2.9.18

Ver. 1.1

D.5 Participant Schedule

D.5.1 Overview

Individuals will be screened over the phone and at one in-person visit. Eligible participants who choose to enroll in the study will attend a total of 4 in-person visits. Participants will be randomized into either the intervention or control group after the screening visit. All study visits will be conducted at the Helfgott Research Institute in Portland, OR. Refer to Table 4 for an outline of the study visits.

Table 4: Study Procedures

	Phone Screening	Screening Visit	Study Visit 1 (Week 1)	Study Visit 2 (Week 5)	Study Visit 3 (Week 9)
Eligibility screening	X				
Consent for study participation		X			
Eligibility verification		X			
Demographic form		X			
W-9		X			
Anthropometrics/Vitals: height, weight, waist-hip ratio, heart rate, blood pressure, temperature, respiratory rate		X	X	X	X
Questionnaires: 
 • NUNM Multi-system Symptom/Adverse Event • MSQ • MYMOP • PROMIS-29 • Lifestyle Habits • VioScreen • Study specific FFQ 			X	X	X
Blood Draw, blood spot card and saliva sample			X	X	X

Protocol

Study Title: Methylation Diet and Lifestyle (MDL) Study

PI: [name], ND, MPH and [name], ND

IRB #: RB100217

Approval Date: 2.9.18

Ver. 1.1

DNA Methylation Pathway Profile - SNP Panel			X		
Infinium Methylation EPIC Index			X		X
Methylation Profile			X	X	X
Folate Vitamer Panel			X	X	X
Estimated Time to Complete	15 minutes	45 minutes	90 minutes	90 minutes	90 minutes

D.5.2. Recruitment

Recruitment will be conducted in the general community surrounding Portland, OR using flyers, online, newspaper, and electronic newsletters.

D.5.3. Telephone Screening

Potential participants will be screened over the phone prior to coming in for the first visit. A standardized telephone script will be used. The telephone screening call will take approximately 10-15 minutes. Participants who meet eligibility criteria over the phone will be scheduled for a screening visit. The consent form will be provided to participants prior to the screening visit via email; they will be instructed to review the form ahead of time but not to sign it until the screening visit where they can ask questions about the study. If an individual is eligible for the study, enrollment will happen on a rolling basis.

D.5.4. Screening Visit

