All study visits will take place at the Helfgott Research Institute in Portland, OR. The objective of the Screening Visit is to explain the study procedures, secure informed consent, and verify eligibility for the trial. Eligibility will be verified by reviewing responses to the eligibility questionnaire. The screening visit is estimated to take 45 minutes.

The following will be performed/obtained at screening:

- Signed and dated informed consent
- Eligibility Questionnaire
- Verification that the participant meets the inclusion and exclusion criteria;
- W-9 – once determined eligible
- Demographics (including age, gender, ethnicity, and race);
- Anthropometrics and vitals (including height, weight, pulse rate, blood pressure);

Protocol

Study Title: Methylation Diet and Lifestyle (MDL) Study
 PI: [name], ND, MPH and [name], ND
 IRB #: RB100217
 Approval Date: 2.9.18

Ver. 1.1

Sample half size servings of the study supplement drink will be provided while participants are completing the eligibility questionnaire. Upon sampling the shakes, participants will be asked if they are willing to take the product twice per day for the study period.

D.5.5. Informed Consent

Consent will be obtained from participants at the beginning of the screening visit. The consent form will include the purpose of the study, a description of the procedures, a list of risks and benefits, an assurance of confidentiality, an assurance of withdrawal without prejudice, a statement about payment policies for research related injuries, study incentives, and a telephone number for answering questions about the research, all explained at an 8th grade reading level. Participants will also be given information on their right to privacy for personal health information based on HIPAA regulations. Procedures for data sharing using de-identified data will be explained later in this protocol.

D.5.6. Randomization

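### Minor safety point: the screening visit offers a taste of the study drink while the eligibility form is still being filled in, so tasting can come before the on-site allergy check is finished

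*Protocol*

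**What the plan says.** Section D.5.4 (Screening Visit) sets the timing of the tasting: "Sample half size servings of the study supplement drink will be provided while participants are completing the eligibility questionnaire". It then gives the purpose: "Upon sampling the shakes, participants will be asked if they are willing to take the product twice per day for the study period". On verification, the same section says: "Eligibility will be verified by reviewing responses to the eligibility questionnaire".

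The exclusion concerned is in D.3.2: "Known sensitivity, intolerance or allergy to ingredients in the study supplements or in the recommended dietary therapy". The tasting serves an inclusion criterion in the same section: "Willing to drink a nutrient-enriched beverage and take a encapsulated probiotic daily".

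Two steps come before the tasting. Section D.5.3 (Telephone Screening) says: "A standardized telephone script will be used", and: "Participants who meet eligibility criteria over the phone will be scheduled for a screening visit". Section D.5.5 (Informed Consent) adds: "Consent will be obtained from participants at the beginning of the screening visit".

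Table 4 places eligibility screening at the telephone stage and eligibility verification at the screening visit. Sections E.1.2 and E.2.2 name the exclusion of men with known reactions to the ingredients, and eligibility screening in general, as protection against the risks of taking the product.

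**The concern.** A check meant to keep men with a known ingredient allergy away from the product should be complete before they swallow any of it. D.5.4 runs the two side by side: the drink is handed over while the man is still writing the answers that staff will later review. The section does make another item wait, since the W-9 tax form is collected only once eligibility is established. The drink has no such condition.

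At stake is one avoidable exposure in an unusual case: a man who knows of an allergy, was not caught by telephone, and does not realise that the drink contains the ingredient. Randomization follows the screening visit (D.5.1), so the tasting also reaches men who will be found ineligible or assigned to control and who would otherwise take no study product during the trial. Power, endpoints and analysis are not involved.

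**Working it through.** The plan states no figure on this point, so the check is mainly one of sequence, with a short calculation of the exposure.

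**Sequence**

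1. Before the visit: the scripted telephone screen (D.5.3). Only men who meet the criteria are given an appointment. The allergy exclusion is one of the criteria, so it has been applied once by self-report.
2. Start of the visit: consent (D.5.5).
3. During the visit: the man fills in the eligibility questionnaire, and the sample is provided in that interval (D.5.4).
4. After the form is filled in: staff can complete their review of the answers (D.5.4; eligibility verification in Table 4).
5. After the tasting: the willingness question (D.5.4).

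Step 3 comes before step 4 can be finished. The text fixes when the sample is provided but not when the man drinks it, and it does not forbid staff from looking at the allergy answers early. The supportable statement is therefore that tasting *can* come before the on-site check is complete, not that it always will. No section requires the allergy answers to be reviewed first.

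**Exposure**

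Inputs are from D.7.1 (PhytoGanix). The assumption is that a half-size serving is half of the serving defined there.

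| Component | Full serving | Half serving |
|---|---|---|
| Powder in total | 10.4 g | 10.4 / 2 = 5.2 g |
| Seed and prebiotic blend | 5.53 g | 5.53 / 2 = 2.765 g |
| Vegetable blend | 2.35 g | 2.35 / 2 = 1.175 g |
| Fruit blend | 1.2 g | 1.2 / 2 = 0.60 g |
| Herbal blend | 300 mg | 300 / 2 = 150 mg |
| Enzyme blend | 200 mg | 200 / 2 = 100 mg |
| *L. acidophilus* | 200 mg | 200 / 2 = 100 mg |

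Named components of the four food and herbal blends: 4 + 8 + 6 + 13 = 31. Some are everyday foods such as apple and carrot. Others are things a man might not expect in a fruit drink, such as shiitake, dong quai and Japanese knotweed. The count shows why a comparison with the list could be useful. It does not measure the probability or severity of a reaction, and the protocol offers nothing from which to estimate either.

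**The case against.** The strongest reply is that the exclusion has already been applied. A man reaches the visit only after meeting the criteria by telephone, and sections E.1.2 and E.2.2 do not say which screening step gives the protection. He has also been emailed the consent form, has had the chance to ask questions, and has signed. The telephone script, the questionnaire and the consent form are not shown, and any of them may already cover the ingredients. Both checks rest on the same man's account of himself, so a second look adds little unless staff compare it with the ingredient list, a comparison the protocol does not describe. The ingredients are described as GRAS and commonly eaten, and the tasting takes place at the research site. The order of two items within a visit could be settled in a checklist.

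Most of this stands, and it is why the point ranks lowest. It does not remove the point, because the protocol itself fixes the overlap and itself asks for verification at the visit.

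Three stronger readings are tempting but not supported:

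- A reader might infer that men taste the drink with no prior allergy screening. D.5.3 shows otherwise.
- A reader might infer that D.5.4 contradicts the safeguards in section E. It does not, since the telephone screen also serves them.
- A reader might take the label contents in the D.7 product descriptions, which list no ingredients, as evidence that the man is uninformed. Those labels concern dispensed product and say nothing about what he is told of a sample served by staff.

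**Conclusion.** The point holds as a minor matter of order. D.5.4 allows a half serving of the study drink to be tasted before staff have finished verifying the allergy, sensitivity and intolerance exclusion at the visit. The residual risk is small, because this is a second check after a telephone screen and consent. It is confined to a known allergy missed by telephone and not connected by the man with the drink. How small depends on the unseen script, questionnaire and consent form; if they already go through the ingredients, little is left. Tasting at this visit is sensible in itself, because willingness to take the product is an entry criterion. Only its place relative to the allergy review is in question. It deserves a wording change because the change is so cheap.

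**What to change.** Reword D.5.4 so that, once consent is signed, staff go through the man's answers on allergy, sensitivity and intolerance and compare them with the PhytoGanix ingredients in D.7.1. Only if nothing is found do they offer the sample and ask whether he would take the product twice a day.

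This is a change of order plus one short added step, since the protocol does not now describe the comparison with the ingredient list. The cost is one sentence of text and a few minutes of the 45-minute visit, because the tasting would no longer overlap with the form. The tasting, the criteria and the rest of the design stay as they are.
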